Patients are treated with octagam®, panzyga® or cutaqui® according to the Investigator's prescription. For dosage recommendations please refer to the local octagam®, panzyga® or cutaqui® package leaflets.

Dosage and duration of treatment is at the sole discretion of the Investigator and will depend on the type and/or severity of the disease and the patient's clinical condition.

In case of SCIG home treatment the Investigator should promote compliance by instructing the patient to take cutaqui[®] exactly as prescribed and by stating that compliance is necessary for the patient's safety. The patient should be instructed to contact the Investigator if he/she is unable for any reason to administer cutaqui[®] as prescribed.

All dosages of octagam[®], panzyga[®] or cutaqui[®] that a patient received during the observation period at the study center are to be recorded on the corresponding eCRF pages. Dosages of cutaqui[®] that a patient administered during the observation period at home are to be recorded in the patient diary and will be entered into the eCRF later. It is of utter importance that all data entered into the diary are checked by the Investigator for completeness and any safety-relevant issues (including infusion site reactions) during each patient's visit to the study center.

Any drug dose adjustment and interruptions should be recorded on the corresponding eCRF page.

If, for any reason, the Investigator or the patient decide to discontinue the treatment with octagam[®], panzyga[®] or cutaqui[®], the observation period of this patient will be terminated. Efforts should be made to arrange a close-out visit. The reason(s) for termination in the eCRF is to be documented. Switching from one Octapharma Ig product to another Octapharma Ig product is possible without termination of the study but should be documented.

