## 6 STATISTICAL CONSIDERATIONS AND ANALYSIS

### 6.1 Derived Variables

The below table provides the list of derived variables for demographic and baseline characteristics, various duration derivations and other important derivations applicable for this study.

Variables	Formula
Demographic and baseline characteristics	
Age at baseline (in years)	Year of the baseline visit – year of birth
Body mass index (BMI) (kg/m  )	Baseline weight (kg)/[height (m)]  . Round to two decimal places.
Derivation of durations	
Study day at any visit	Date of interest – date of first IVIG/SCIG infusion. One day is added if this difference is $\geq 0$
Treatment duration (in months)	(Date of last infusion with IVIG/SCIG – Date of first infusion with IVIG/SCIG + 1)/30.4375. Round to one decimal place.
Study duration (in months)	(Maximum(Date of close-out visit, date of last infusion with IVIG/SCIG) - Date of first infusion with IVIG/SCIG + 1)/30.4375. Round to one decimal place.
Derivation of exposure related measures	
Dose per infusion (g)	Infusion volume (mL) x strength where strength = 0.05 for octagam® 5% strength = 0.1 for octagam® 10% and panzyga® strength = 0.165 for cutaqui®
Dose per infusion (g/kg body weight)	Dose per infusion (g)/weight (kg), weight as measured at the respective infusion visit. Round to two decimal places.
Maximum infusion rate (mL /kg body weight/hr)	See section 7.4.2 for necessary transformations. Round to two decimal places.

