### 7.4.2 Exposure to study drug

For each patient the following measures will be calculated and summarized with descriptive statistics by treatment group and overall in the Safety population:

- Number of IVIG/SCIG infusions.
- Number of IVIG/SCIG infusion courses. An infusion course is defined as a sequence of infusions that are given over consecutive days with allowed gaps of 3 days without

documented infusions, i.e. a new course starts when there are at least 4 days without documented infusions.

- Complete dose (in g and g/kg body weight).
- Mean dose per infusion (in g and g/kg body weight).
- Mean dose per infusion course (in g and g/kg body weight).
- Average infusion rate (in mL/kg body weight/hr).
- Maximum infusion rate (in mL/kg body weight/hr).

In the eCRF only the volume (in mL) of an infusion is captured. To calculate doses in grams the following transformations will be applied:

For octagam® 5% the dose in grams per infusion will be calculated as infusion volume (mL) x 0.05 as octagam® 5% contains 50 mg protein per mL of solution. For octagam® 10% the dose in grams per infusion will be calculated as infusion volume (mL) x 0.1 as octagam® 10% contains 100 mg protein per mL of solution. Panzyga® comes as a 10% solution ready for intravenous administration; hence the dose in grams per infusion will also be calculated as infusion volume (mL) x 0.1. Cutaquig® is a sterile solution of human normal immunoglobulin containing 16.5% (165 mg/mL) protein, hence the dose in grams per infusion will be calculated as infusion volume (mL) x 0.165. To get the dose per kg body weight the dose in grams will be divided by the body weight (in kg) as determined at the respective infusion visit. In case the weight is missing the following rules will be applied:

- (i) Use the weight measured at the latest preceding infusion visit.
- (ii) If no weight measurements are made at any preceding infusion visit use the weight from the first visit on which weight was measured.

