For each patient the complete dose (in g or g/kg body weight) is calculated as sum of the doses (in g or g/kg body weight) over all infusions and the mean dose per infusion (in g or g/kg body weight) as arithmetic mean of the doses (in g or g/kg body weight) over all infusions. The mean dose per infusion course (in g or g/kg body weight) is defined by (i) summing up all doses (in g or g/kg body weight) over an infusion course and then (ii) calculating the arithmetic mean of these summed-up doses over all infusion courses.

The infusion rate (in mL /kg body weight/hr) per single infusion will be calculated as infusion volume (mL)/(duration of infusion (hr) x weight (kg)), missing weights will be imputed as described above. The average infusion rate for a patient will be determined as the arithmetic mean of the infusion rates over all infusions.

For each infusion visit, the maximum infusion rate is recorded in the eCRF. Maximum infusion rates can be reported in four different units: mL/min, mL/hr, mL/kg body weight/min, and mL/kg body weight/hr. The following transformations will be applied to get the maximum infusion rate in mL/

kg body weight/hr:

Original Unit	Transformation
mL/min	x 60 / weight (kg)
mL/hr	/ weight (kg)
mL/kg body weight/min	x 60
mL/kg body weight/hr	No transformation necessary

Missing weights will be imputed as described above. For the tabulation the maximum of the maximum infusion rate over all infusions will be determined for each patient.

All summaries of exposure measures will also be generated by diagnosis.

All infusion details as recorded in the eCRF will be listed.

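### SAP 6.1, read literally, rounds each infusion's g/kg dose before 7.4.2 sums and averages it; the SAP should say that unrounded values are used

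*SAP*

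**What the plan says.** The table of derived variables in SAP 6.1 has a formula column. For dose per infusion in g/kg the formula reads "Dose per infusion (g)/weight (kg), weight as measured at the respective infusion visit. Round to two decimal places". Dose per infusion in grams, the row above it, has no rounding instruction.

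SAP 7.4.2 uses the per-infusion dose as a building block. A patient's complete dose "is calculated as sum of the doses (in g or g/kg body weight) over all infusions", and the section defines "the mean dose per infusion (in g or g/kg body weight) as arithmetic mean of the doses" over all infusions. Mean dose per infusion course sums the doses within each course and then averages over courses. No rounding step is mentioned in any of these.

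The same section describes the g/kg dose a second time, also without rounding: "To get the dose per kg body weight the dose in grams will be divided by the body weight (in kg"), with weight taken at the respective infusion visit. If that weight is missing, the first rule is "Use the weight measured at the latest preceding infusion visit". For the subcutaneous product, "hence the dose in grams per infusion will be calculated as infusion volume (mL) x 0.165".

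Neither document gives an SCIG volume or g/kg dose. Protocol 4.1 says "Dosage and duration of treatment is at the sole discretion of the Investigator".

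**The concern.** For BMI, treatment duration and study duration, rounding in SAP 6.1 is harmless to later dose derivations because nothing is summed from them. The g/kg dose per infusion is different: it is an intermediate quantity that feeds three further derivations. A programmer who creates the variable as 6.1 defines it and then follows 7.4.2 will sum rounded numbers.

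A step of 0.01 g/kg is fine for a large intravenous infusion but coarse for a small, frequent subcutaneous one. A patient who receives the same volume at a steady weight gets the same rounding error every time. Carrying weights forward reinforces this. The diary items listed for home treatment in Protocol 3.1.3 do not include weight, so home infusions may often rely on a carried-forward value.

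At stake are the g/kg exposure tables, which are reported by treatment group and by diagnosis with median, minimum and maximum, and the patient listings of derived data. The error would fall mainly on one product, and two programmers could obtain different tables from the same data.

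**Working it through.** The plan states no figure for this point, so there is nothing to reproduce; the check is direct arithmetic.

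**Inputs from the documents.** SCIG strength 0.165 g/mL and 10% IVIG strength 0.1 g/mL (SAP 6.1 and 7.4.2); rounding to two decimals (SAP 6.1).

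**Assumed inputs.** Infusion volumes, body weights and infusion frequency.

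**Formulas.** True dose d = volume × strength / weight. Rounded dose r = d to two decimals. Relative error = (r − d)/d. Because |r − d| ≤ 0.005 g/kg, the relative error is at most 0.005/d. Over n infusions at constant d, the complete dose is n·r instead of n·d, so the relative error of the sum and of the mean is again (r − d)/d. It does not shrink with n.

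**Bound, free of assumptions about volume and weight.**

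| True dose per infusion (g/kg) | 0.005/d |
|---|---|
| 0.015 | 33% |
| 0.025 | 20% |
| 0.05 | 10% |
| 0.10 | 5% |
| 0.20 | 2.5% |
| 0.40 | 1.25% |

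**Examples with assumed volume and weight.**

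| Infusion | d (g/kg) | r (g/kg) | Error |
|---|---|---|---|
| SCIG 10 mL, 60 kg | 1.65/60 = 0.0275 | 0.03 | +9.1% |
| SCIG 10 mL, 66.5 kg | 1.65/66.5 = 0.0248 | 0.02 | −19.4% |
| SCIG 10 mL, 70 kg | 1.65/70 = 0.0236 | 0.02 | −15.2% |
| SCIG 10 mL, 80 kg | 1.65/80 = 0.0206 | 0.02 | −3.0% |
| SCIG 20 mL, 66 kg | 3.30/66 = 0.0500 | 0.05 | 0% |
| SCIG 20 mL, 75 kg | 3.30/75 = 0.0440 | 0.04 | −9.1% |
| SCIG 48 mL, 70 kg | 7.92/70 = 0.1131 | 0.11 | −2.8% |
| 10% IVIG 300 mL, 70 kg | 30/70 = 0.4286 | 0.43 | +0.3% |

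For 10 to 20 mL at 60 to 80 kg, the error therefore runs from nil to just under 20%, depending on where d falls between two steps.

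**Accumulation.** At 10 mL daily and 70 kg for 365 days, the unrounded sum is 365 × 1.65/70 = 8.60 g/kg. The sum of rounded values is 365 × 0.02 = 7.30 g/kg. The gram total is 365 × 1.65 = 602.25 g, and 602.25/70 = 8.60, so in this constant-weight case the two exposure columns would disagree.

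**Does it cancel?** A simulation assumed weights of about N(75, 15) kg, 52 infusions per patient and a within-patient weight SD of 1 kg.

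| SCIG volume | Median patient error | Worst patient |
|---|---|---|
| 10 mL | 8.4% | 32% |
| 20 mL | 4.3% | 17% |
| 48 mL | 1.1% | 5% |

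Bias in the group mean was about 0.1% or less at each volume. Errors cancel across many patients but not within one.

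**The case against.** The strongest reply is that the SAP never says rounding comes first. SAP 7.4.2, the section that defines the exposure measures, gives the g/kg dose as a plain quotient and sums the doses without mentioning rounding. The rounding phrase in 6.1 is also attached to BMI and the durations, where it can be taken as reporting precision. This stands in part. A reader might infer that the plan definitely rounds before summing; the documents support that as the literal reading of 6.1 with 7.4.2, not as an explicit instruction.

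A reader might also take 20% as the maximum error. It is neither a figure from the documents nor a bound. It belongs to a dose near 0.025 g/kg; the bound is higher for smaller doses and 5% or less from 0.10 g/kg upward.

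Three further objections stand.

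- For mean dose per infusion the absolute error cannot exceed 0.005 g/kg. If that row is displayed to two decimals, rounding at the end loses much the same information. The order of rounding matters mainly for complete dose and dose per course.
- Maximum infusion rate is also rounded in 6.1, and a reader might want the same change there. It is not needed: the patient's value is a maximum over infusions, and the maximum of rounded values equals the rounded maximum.
- Total grams divided by one weight need not equal total g/kg even without rounding, because 7.4.2 uses the weight at each visit. The mismatch is a clean sign of error only when weight is constant.

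The consequences are also limited. The study is descriptive, exposure is not an endpoint, each g/kg dose summary has a gram counterpart with no rounding rule, and all infusion details are listed, so correct values can be recovered.

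**Conclusion.** The point holds as a gap in specification that, under the literal reading, gives wrong patient-level g/kg doses. The certain part is the bound: up to 0.005 g/kg per infusion, or 0.005/d in relative terms, with the same sign at every infusion for a patient on stable volume and weight. The practical size rests on assumed SCIG volumes and weights. For infusions of 10 to 20 mL at 60 to 80 kg, errors of about 9% to 15% in a patient's complete dose are plausible; some combinations give almost none and a few approach 20%. For larger SC volumes and for IVIG-sized doses the error is a few percent or less.

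The effect is confined to individual values, medians, ranges and small groups in the g/kg exposure tables. The documents do not say how many patients receive the SC product or how small the diagnosis groups will be, so the effect there cannot be quantified. The documents do not support reading this as a bias in group means by product, in gram-based exposure or in the primary endpoint, ADR incidence, which does not use the g/kg dose.

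**What to change.** In SAP 6.1, at dose per infusion (g/kg), and again in 7.4.2, state that unrounded per-infusion g/kg values enter all sums and means, including dose per course, and that rounding applies only to displayed results. This removes the accumulated error and settles the order of operations under either reading.

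The cost is one sentence. No data collection changes, and programming is no heavier. Maximum infusion rate can stay as written, and display units and decimals can be left to the table, figure and listing templates.

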### 6.2 Handling of missing data and outliers

#### 6.2.1 Missing data analysis methods

For the handling of missing numbers of infections, see sections 7.3.2 and 7.5.2. Missing values of body weight in the calculation of measures of exposure will be handled as described in section 7.4.2. Otherwise, missing data will not be imputed for any analysis. For the handling of missing or incomplete start and end dates of Individual Case Safety Reports and medications, see section 6.2.2.

### **6.2.2 Handling of missing or incomplete dates**

For the determination whether an Individual Case Safety Report (ICSR, see section 7.6.1 for the definition) as denoted on the ADR form that has a missing or incomplete start date might not qualify as on-study-case the following rules will be applied:

#### **If only the day of ICSR start date is missing:**

If the ICSR start year and month are the same as that for the first infusion date, then:

- If the full (or partial) ICSR end date is not before the first dose date or ICSR end date is missing, then impute the ICSR start day as the day of first dose date; otherwise, impute the ICSR start day as 1.
- Otherwise, if the full (or partial) ICSR end date is before the first dose date, then impute the ICSR start day as 1.

Compare the imputed ICSR start date with the first infusion date to determine whether the ICSR actually occurred before the first dose or can be evaluated as on-study ICSR.

#### **If day and month of ICSR start date are missing:**

If ICSR start year = first dose year, then:

- If the full (or partial) ICSR end date is not before the first infusion date or the ICSR end date is missing, then impute the ICSR start month and day as the month and day of the first infusion date; otherwise, impute the ICSR start month as January and the start day as 1.
- Otherwise, if the full (or partial) ICSR end date is before the first dose date, then impute the ICSR start month as January and the start day as 1.

Compare the imputed ICSR start date with the first infusion date to determine whether the ICSR actually occurred before the first dose or can be evaluated as on-study ICSR.

#### **If the year of ICSR start date is missing:**

If the year of the ICSR start date is missing or the ICSR start date is completely missing, then compare the full (or partial) ICSR end date to the first infusion date. If the ICSR end date is before the first dose date, then the ICSR will not be considered as on-study ICSR. Otherwise, the ICSR will be considered as on-study ICSR.

Imputation rules for missing or partial medication start/stop dates are defined below:

#### **Missing or partial medication start date:**

- If only the day is missing, use the first day of the month.
- If day and month are both missing, use the first day of the year.

---

- If day, month and year are all missing, use a date before the minimum of the first infusion date and the medication stop date.

**Missing or partial medication stop date:**

- If only the day is missing, use the last day of the month.
- If day and month are both missing, use the last day of the year.
- If day, month and year are all missing, assign ‘continuing’ status to stop date

Note that these imputation rules are only applied to determine the status of an ICSR or medication in relation to the treatment phase of the study. Imputed dates are not to be used in any patient listings.

Property of Octapharma. Do not copy or distribute without written permission.

## **7 STATISTICAL METHODS**

### **7.1 General statistical conventions**

All statistical procedures will be completed using SAS version 9.4 or higher.

Continuous variables will be summarized using descriptive statistics, including number of subjects (n), mean, median, standard deviation (SD), minimum and maximum.

For categorical variables, summaries will include counts of patients and percentages. Percentages will be rounded to one decimal place.

All summaries will be presented by treatment group and overall, unless otherwise specified. As patients are allowed to change the study drug during the course of the study, treatment groups can be defined that are composed of more than one treatment depending on which patterns of treatment change will actually be observed. In case that such treatment groups are defined, summary tables by visit or summary tables for events that occur within the study will contain more than one column for these composed treatment groups. A patient will be summarized in the column that belongs to the actual treatment that the patient received at the respective visit or at the onset of the respective event.

All patient data, including those derived, will be presented in individual patient data listings. Unless otherwise stated, unscheduled visit results will be included in date/time chronological order, within patient listings only. All listings will be sorted by centre, patient number, date/time and visit (if applicable). The treatment group as well as patient's sex, age and diagnosis will be stated on each listing. Unless otherwise stated, data listings will be based on the Safety population.

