### 3.5 Secondary endpoint(s)

Secondary endpoint in this study is the efficacy of the IVIG/SCIG measured as:

For patients with diagnosis primary immunodeficiency (PID) or secondary immunodeficiency (SID):

- For each fourth infusion visit (starting with infusion visit 4) and the close-out visit: Influence of the treatment with IVIG/SCIG on the frequency, intensity and duration of infections and the consumption of antibiotics since the last visit.
- For each fourth infusion visit (starting with infusion visit 4) and the close-out visit: Occurrence of infectious episodes since the last visit.

For patients with other diagnoses than PID or SID:

- For each infusion visit and the close-out visit: Development of the clinical appearance of disease since the last visit.

---

- At the close-out visit: Influence of IVIG or SCIG treatment on the course of the disease.

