### 7.5.2 Analysis of efficacy endpoint(s)

#### For patients with diagnosis PID or SID:

For each fourth infusion visit (starting with infusion visit 4) and the close-out visit the influence of the treatment with IVIG/SCIG on the frequency, intensity and duration of infections and the consumption of antibiotics since the last visit is recorded. Possible outcomes are beneficial, unchanged and unfavorable. Counts and percentages of these outcomes will be summarized by infusion visit and for the close-out visit by treatment group and overall in the Safety population. In addition, the patient's last available assessments will be summarized. These summaries will be generated for the pool of PID/SID patients and for each of the two diagnoses separately.

For each fourth infusion visit (starting with infusion visit 4) and the close-out visit the occurrence of new infectious episodes (yes/no) since the last visit is recorded. In case of the occurrence of new infectious episodes patients are asked regarding the infected area and the number of infectious episodes in this area using the following pre-specified categories:

- Serious infections of the upper respiratory tract

- Serious infections of the lower respiratory tract
- Urinary tract infections
- Bacteremia/sepsis
- Bacterial meningitis
- Osteomyelitis/septic arthritis
- Bacterial pneumonia
- Visceral abscesses
- Other infectious diseases

The number and percentage of patients with new infectious episodes since the last visit and the number and percentage of patients with new infectious episodes in each of the above categories will be summarized by infusion visit and for the close-out visit by treatment group and overall in the Safety population. In addition, this summary will be generated for the patient's last available assessment.

Further the occurrence of any infectious episodes during the course of the study, the occurrence of any infectious episodes in each of the above categories during the course of the study, the total number of infectious episodes and the total number of infectious episodes in each of the above categories will be summarized by treatment group and overall in the Safety population. These summaries will be generated for the pool of PID/SID patients and for each of the two diagnoses separately.

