**For patients with diagnoses different from PID or SID:**

At each infusion visit and the close-out visit patients with diagnoses other than PID or SID are asked regarding the development of the disease since the last visit. Possible outcomes are improved, not changed and deteriorated. The number and percentage of patients with these outcomes at each infusion visit and the close-out visit will be summarized by treatment group and overall in the Safety population. In addition, this summary will be generated for the patient's last available assessment.

At the close-out visit, patients with diagnoses other than PID or SID are also asked regarding the influence of IVIG/SCIG treatment on the course of the disease. Possible outcomes are beneficial, unchanged and unfavorable. The number and percentage of patients with these outcomes will be summarized by treatment group and overall in the Safety population.

These summaries will be generated for the pool of non-PID/SID patients and for each of the pre-specified diagnoses (see section 7.3.2) separately.

All efficacy outcomes will be listed.

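### In the by-visit columns for patients who switch product, SAP 7.1 files efficacy answers about the preceding interval under the product given at the visit, so the first answer at or after a switch can sit under the wrong product

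*SAP*

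**What the plan says.** Protocol 4.1 allows a change of product within the study: "Switching from one Octapharma Ig product to another Octapharma Ig product is possible without termination of the study". SAP 5.2 and 7.1 allow for this by letting treatment groups be composed of more than one product, depending on the switch patterns seen.

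SAP 7.1 then gives a column rule that applies only to those groups. "In case that such treatment groups are defined, summary tables by visit or summary tables for events that occur within the study" are to have more than one column for each composed group. The column is chosen as follows: "A patient will be summarized in the column that belongs to the actual treatment that the patient received at the respective visit", and the sentence goes on "or at the onset of the respective event".

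The repeated efficacy items look backward:

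- Diagnoses other than PID/SID (SAP 7.5.2): at every infusion visit and at close-out, patients "are asked regarding the development of the disease since the last visit".
- PID/SID (SAP 7.5.2): at every fourth infusion visit and at close-out, the influence of treatment on infections and "the consumption of antibiotics since the last visit is recorded". New infectious episodes are asked over the same window.

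All are tabulated by visit and treatment group. SAP 3.5 adds one whole-course rating for patients without PID or SID: "At the close-out visit: Influence of IVIG or SCIG treatment on the course of the disease".

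Neither SAP 7.5.2 nor SAP 8 has a separate attribution rule for items that look back.

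**The concern.** The column rule suits data that belong to the visit itself, such as dose or infusion rate. It does not suit an answer about the interval that ended at the visit. When product B is first given, the answer just collected is about time on product A, but the rule puts it in column B.

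At close-out the rule gives no answer at all. Table 1 (Protocol 3.1.3, SAP 3.3) schedules no treatment details there, so no product is received at that visit, yet look-back items are collected.

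The secondary objective is to document efficacy, and SAP 7.5.1 limits its analysis to descriptive statistics. No model or test downstream would correct a wrongly placed answer. The assessment affected is also the one closest to the decision to switch.

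**Working it through.** The plan gives no figure on this point to reproduce: SAP 4 states 300-500 patients without a calculation, and no switch rate is given. The check is an enumeration.

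**Set-up.** Let the first infusion of the new product be at infusion visit *j*, and let the next efficacy assessment be at visit *A* ≥ *j*. Count the interval from visit *i* to visit *i*+1 as time on the product given at visit *i*. The old-product share of the window is the number of its intervals with *i* < *j*, divided by the number of intervals in it. Under SAP 7.1 the assessment at *A* goes into the new product's column whatever this share is.

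**Diagnoses other than PID/SID.** Every infusion visit is assessed, so *A* = *j*. The window is the single interval from *j*−1 to *j*, and the product given at *j*−1 is the old one. The share is 1/1 = 100%. If the patient then has *m* infusion visits in the new product's column (counting the switch visit), 1 of *m* is misfiled. For assumed values *m* = 1, 3, 6 and 12 this is 100%, 33%, 17% and 8%.

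**PID/SID.** Assessments fall at infusion visits 4, 8, 12 and so on. The SAP does not say whether the last visit is the previous assessment or the preceding infusion visit, so both are shown for the assessment at visit 8:

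| First new-product infusion | Share if window is visits 4 to 8 | Share if window is visits 7 to 8 |
|---|---|---|
| Visit 5 | 1/4 = 25% | 0% |
| Visit 6 | 2/4 = 50% | 0% |
| Visit 7 | 3/4 = 75% | 0% |
| Visit 8 | 4/4 = 100% | 1/1 = 100% |

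On the first reading the mean is (1 + 2 + 3 + 4)/16 = 62.5%, assuming equal intervals and equally likely switch positions. On the second, one switch position in four is wholly misfiled and the other three are filed correctly. Later blocks of four visits behave in the same way.

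**Can the onset clause rescue the rule?** It assigns events to the product in use when they began, which works for ADRs. A rating such as improved/not changed/deteriorated or beneficial/unchanged/unfavorable has no onset. For infections, SAP 7.5.2 mentions only the area and the number of episodes, with no onset date, and tabulates new episodes by visit.

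**The case against.** The strongest reply is that the rule's reach is narrow. It acts only if composed groups are defined, and only on the columns inside them. A reader might infer that the single-product octagam, panzyga and cutaquig groups absorb each other's outcomes. The text does not support that: switchers in a composed group are kept apart from single-product patients. If no composed group is formed, the rule is not triggered. SAP 5.2 then says only that patients are analysed by the treatment actually received, which is a different gap. This part of the objection stands.

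A reader might also infer that the whole-course close-out rating is misattributed. SAP 7.5.2 tabulates it by treatment group, once per patient, so a switcher can naturally stay in the composed group. That needs only confirmation.

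Three further limits stand. Only the first assessment after each switch is affected. The 62.5% holds on one reading of the last visit, and on the other reading most switch positions cause no error. A switch to cutaquig may begin at home and be recorded in a diary (Protocol 3.1.3 and 4.1). The documents do not say whether a home infusion counts as an infusion visit, so such a window may be mixed and not wholly old-product time.

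Infusion details and efficacy outcomes are listed (SAP 7.4.2, 7.5.2), so individual answers can be traced. But a listing does not correct a summary table. None of these points supplies a rule for look-back items.

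**Conclusion.** The mismatch follows from the plan's own definitions. Within a composed group's by-visit efficacy columns, the first assessment at or after a switch can describe the old product and be reported under the new one. The affected window is 100% old-product time for patients without PID or SID whose new product starts at an assessed infusion visit. For PID/SID it is 25 to 100%, or 0 or 100%, depending on an undefined term. At close-out the rule yields no column for the look-back items.

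The consequence is limited to descriptive secondary tables for switchers. The overall column is unaffected, and so is the primary ADR endpoint, because ADRs are assigned at onset.

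It is tempting to add a direction, for example that a deterioration prompting a switch is charged to a product not yet given. The documents state neither why nor how often patients switch, so neither the direction nor the number of patients affected can be derived. The percentages rest on counting each interval as time on the product given at its start; the 62.5% mean also needs equal intervals and equally likely switch positions.

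**What to change.** In SAP 7.1, keep the current rule for exposure data and for ADRs at onset, and add a rule for look-back efficacy items along these lines:

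> Efficacy items that refer to the time since the last visit, including those at close-out, are attributed to the product administered from the visit that opens the window up to, but not including, the current visit. Windows containing more than one product are shown in a separate mixed column.

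Two clarifications belong with it:

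- In SAP 7.5.2, state for PID/SID whether the last visit is the previous fourth-visit assessment or the preceding infusion visit.
- Confirm that a switcher's whole-course close-out rating appears only under the composed group and overall.

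In the PID/SID example, if the window is visits 4 to 8, switches at visits 5 to 7 would go to the mixed column and a switch at visit 8 to the old product. If the window is visits 7 to 8, only the switch at visit 8 changes column. At infusion visit 1 no study product precedes the answer, so the text should say how an answer recorded there is shown.

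The cost is SAP wording, a lag in the programming and one extra column. Administration dates and treatment details are already in the eCRF (Protocol 3.1.3), so no new data are needed.
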